12. ADVERSE EVENT REPORTING

Timely, accurate, and complete reporting and analysis of safety information from clinical studies are crucial for the protection of subjects, investigators, and the Sponsor, and are mandated by regulatory agencies worldwide. The Sponsor has established Standard Operating Procedures (SOPs) in conformity with regulatory requirements worldwide to ensure appropriate reporting of safety information; all clinical studies conducted by the Sponsor or its affiliates will be conducted in accordance with those procedures.

12.1. Definitions

12.1.1. Adverse Event Definitions and Classifications

Adverse Event

An adverse event (AE) is any untoward medical occurrence in a clinical study subject administered a medicinal (investigational or non-investigational-) product. An AE does not necessarily have a causal relationship with the treatment. An AE can therefore be any unfavorable and unintended sign (including an abnormal finding), symptom, or disease temporally associated with the use of a medicinal (investigational or non-investigational) product, whether or not related to that medicinal (investigational or non-investigational) product. (Definition per International Council for Harmonization- [ICH]).

This includes any occurrence that is new in onset or aggravated in severity or frequency from the baseline condition, or abnormal results of diagnostic procedures, including laboratory test abnormalities.

Note: The Sponsor collects AEs starting with the signing of the ICF (refer to Section 12.3.1 for time of last AE recording).

Serious Adverse Event

A serious AE (SAE) based on ICH and EU Guidelines on Pharmacovigilance for Medicinal Products for Human Use is any untoward medical occurrence that at any dose:

- Results in death
- Is life-threatening
(The subject was at risk of death at the time of the event. It does not refer to an event that hypothetically might have caused death if it were more severe.)
- Requires inpatient hospitalization or prolongation of existing hospitalization
- Results in persistent or significant disability/incapacity
- Is a congenital anomaly/birth defect
- Is a suspected transmission of any infectious agent via a medicinal product
- Is medically important*

*Medical and scientific judgment should be exercised in deciding whether expedited reporting is also appropriate in other situations, such as important medical events that may not be immediately life threatening or result in death or hospitalization but may jeopardize the subject or may require intervention to prevent any of the other SAE outcomes listed above. These should usually be considered serious.

If a serious and unexpected AE occurs for which there is evidence suggesting a causal relationship between the study drug and the event (eg, death from anaphylaxis), the event must be reported as a serious and unexpected suspected adverse reaction even if it is a component of the study endpoint (eg, all-cause mortality).

Unlisted (Unexpected) Adverse Event/Reference Safety Information

An AE is considered unlisted if the nature or severity is not consistent with the applicable product reference safety information. For guselkumab, the expectedness of an AE will be determined by whether or not it is listed in the package insert/summary of product characteristics (SmPC TREMFYA®).

Adverse Event Associated With the Use of the Drug

An AE is considered associated with the use of the drug if the attribution is possible, probable, or very likely by the definitions listed in Section 12.1.2.

12.1.2. Attribution Definitions

Not Related

An AE that is not related to the use of the drug.

Doubtful

An AE for which an alternative explanation is more likely, eg, concomitant drug(s), concomitant disease(s), or the relationship in time suggests that a causal relationship is unlikely.

Possible

An AE that might be due to the use of the drug. An alternative explanation, eg, concomitant drug(s), concomitant disease(s), is inconclusive. The relationship in time is reasonable; therefore, the causal relationship cannot be excluded.

Probable

An AE that might be due to the use of the drug. The relationship in time is suggestive (eg, confirmed by dechallenge). An alternative explanation is less likely, eg, concomitant drug(s), concomitant disease(s).

Very Likely

An AE that is listed as a possible adverse reaction and cannot be reasonably explained by an alternative explanation, eg, concomitant drug(s), concomitant disease(s). The relationship in time is very suggestive (eg, it is confirmed by de-challenge and re-challenge).

12.1.3. Severity Criteria

An assessment of severity grade will be made using the following general categorical descriptors:

Mild: Awareness of symptoms that are easily tolerated, causing minimal discomfort and not interfering with everyday activities.

Moderate: Sufficient discomfort is present to cause interference with normal activity.

Severe: Extreme distress, causing significant impairment of functioning or incapacitation. Prevents normal everyday activities.

The investigator should use clinical judgment in assessing the severity of events not directly experienced by the subject (eg, laboratory abnormalities).

12.2. Special Reporting Situations

Safety events of interest on a Sponsor study drug that may require expedited reporting or safety evaluation include, but are not limited to:

- Overdose of a Sponsor study drug
- Suspected abuse/misuse of a Sponsor study drug
- Accidental or occupational exposure to a Sponsor study drug
- Any failure of expected pharmacologic action (ie, lack of effect) of a Sponsor study drug
- Unexpected therapeutic or clinical benefit from use of a Sponsor study drug
- Medication error involving a Sponsor product (with or without subject exposure to product)
- Exposure to a Sponsor study drug from breastfeeding.

Special reporting situations should be recorded in the CRF. Any special reporting situation that meets the criteria of an SAE should be recorded on the SAE page of the CRF.

12.3. Procedures

12.3.1. All Adverse Events

All AEs and special reporting situations, whether serious or non-serious, will be reported from the time a signed and dated ICF is obtained until completion of the subject's last study-related procedure, which may include contact for follow-up of safety. SAEs, including those spontaneously reported to the investigator within 12 weeks after the last dose of study drug, must be reported using the SAE Form. The Sponsor will evaluate any safety information that is spontaneously reported by an investigator beyond the time frame specified in the protocol. All events that meet the definition of an SAE will be reported as SAEs, regardless of whether they are protocol-specific assessments.

All AEs, regardless of seriousness, severity, or presumed relationship to study drug, must be recorded using medical terminology in the source document and the CRF. Whenever possible, diagnoses should be given when signs and symptoms are due to a common etiology (eg, cough, runny nose, sneezing, sore throat, and head congestion should be reported as "upper respiratory infection"). Investigators must record in the CRF their opinion on relationship of the AE to study therapy. All measures required for AE management must be recorded in the source document and reported according to Sponsor instructions.

The Sponsor assumes responsibility for appropriate reporting of AEs to the regulatory authorities. The Sponsor will also report to the investigator (and the head of the investigational institute where required) all suspected unexpected serious adverse reactions (SUSARs). The investigator (or Sponsor where required) must report SUSARs to the appropriate Independent Ethics Committee/Institutional Review Board (IEC/IRB) that approved the protocol unless otherwise required and documented by the IEC/IRB. A SUSAR will be reported to regulatory authorities unblinded. Participating investigators and IEC/IRB will receive a blinded SUSAR summary, unless otherwise specified.

Subjects must be provided with a "wallet (study) card" and instructed to carry this card with them for the duration of the study indicating the following:

- Study number
- Statement, in the local language(s), that the subject is participating in a clinical study
- Investigator's name and 24-hour contact telephone number
- Local Sponsor's name and 24-hour contact telephone number (for medical staff only)
- Site number and subject number
- Any other information that is required to do an emergency breaking of the blind.

12.3.2. Serious Adverse Events

All SAEs occurring during the study must be reported to the appropriate Sponsor contact person by study-site personnel within 24 hours of their knowledge of the event.

Information regarding SAEs will be transmitted to the Sponsor using the SAE Form, which must be completed and signed by a physician from the study site, and transmitted to the Sponsor within 24 hours. The initial and follow-up reports of an SAE should be made by facsimile (fax).

All SAEs that have not resolved by the end of the study, or that have not resolved upon discontinuation of the subject's participation in the study, must be followed until any of the following occurs:

- The event resolves
- The event stabilizes
- The event returns to baseline, if a baseline value/status is available
- The event can be attributed to agents other than study drug or to factors unrelated to study conduct
- It becomes unlikely that any additional information can be obtained (subject or health care practitioner refusal to provide additional information, lost to follow-up after demonstration of due diligence with follow-up efforts).

Suspected transmission of an infectious agent by a medicinal product will be reported as an SAE.

Any possible Hy's law case (AST or ALT $\geq 3 \times$ ULN together with bilirubin $\geq 2 \times$ ULN or INR >1.5) is considered an important medical event and must be reported to the sponsor in an expedited manner using the Serious Adverse Event form, even before all other possible causes of liver injury have been excluded. The INR criterion is not applicable to participants receiving anticoagulants.

Any event requiring hospitalization (or prolongation of hospitalization) that occurs during the course of a subject's participation in a study must be reported as an SAE, except hospitalizations for the following:

- Hospitalizations not intended to treat an acute illness or AE (eg, social reasons such as pending placement in long-term care facility)
- Surgery or procedure planned before entry into the study (must be documented in the CRF). Note: Hospitalizations that were planned before the signing of the ICF, and where the underlying condition for which the hospitalization was planned has not worsened, will not be considered SAEs. Any AE that results in a prolongation of the originally planned hospitalization is to be reported as a new SAE.

The cause of death of a subject in a study within 12 weeks of the last dose of study drug, whether or not the event is expected or associated with the study drug, is considered an SAE.

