Synopsis, 11.9 Statistical Analyses per Study Part	Description of Change: Two interim analyses of study part 3 were added. They are planned after all subjects have completed their visit at week 116 (or at week 144 in case of subjects entering the re-treatment arm in week 116) and at week 164 (or at week 192 in case of subjects entering re-treatment arm in week 164). The final analysis will be performed after all subjects have completed their visit at week 220 (or at week 248 in case of subjects entering the re-treatment arm in week 220).
	Rationale: To allow two interim analyses of study part 3
10.2 Discontinuation of Study Treatment, 12.3.2. Serious Adverse Events, Appendix	Description of Change: Section 10.2 was adapted to include that study treatment must be discontinued in case of abnormal liver tests. Corresponding appendices (8A and 8B) were added to provide liver stopping criteria and guidance for follow-up assessments. Section 12.3.2 was adapted to emphasize that any possible Hy's law case (AST or ALT \geq 3x ULN together with bilirubin \geq 2X ULN or INR >1.5) has to be reported to the sponsor in an expedited manner using the Serious Adverse Event form.
	Rationale: To incorporate Hy's law language into the protocol

Amendment 4 (15 June 2020)

Overall Rationale for the Amendment: To add an additional exclusion criterion for patients with confirmed or potential SARS-CoV-2 infection. Changes from COVID-19 related Amendment 3 were included in the full protocol.

Section Number and Name	Description of Changes and Brief Rationale
Synopsis; 6. Dosing and Administration	
Description of Change: Added text to allow subcutaneous injections of study drug to be self-administered outside a study site, in cases where a study site visit is not possible, provided those subjects have appropriate experience or have received adequate training to perform self-administration of SC injections.
 
Rationale: To provide flexibility of dose administration in cases where a study site visit is not possible.

5.2 Exclusion Criteria	
Description of Change: Added exclusion criterion 40, to document exclusion of patients with confirmed or suspected SARS-CoV-2 infection or who have had close contact with a person with confirmed or suspected SARS-CoV-2 infection within 6 weeks before baseline and to provide COVID-19-related guidance on study participation and exclusion.
 
Rationale: To exclude patients with confirmed or potential SARS-CoV-2 Infection.

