
 • Immediately discontinue study intervention • Report the event to the sponsor within 24 hours • Complete the liver event reporting form and complete an SAE CRF if the event also met the criteria for an SAE² • Perform follow-up assessments as described in the Follow up Assessment column • Monitor the participant until liver chemistry test abnormalities resolve, stabilize, or return to baseline 
MONITORING:
 
If ALT or AST $\geq 3 \times \text{ULN}$ AND total bilirubin $\geq 2 \times \text{ULN}$ or INR > 1.5:
 
 • Repeat liver chemistry tests (include ALT, aspartate transaminase [AST], alkaline phosphatase, total bilirubin and INR) and perform liver event follow-up assessments within 24 hours • Monitor participant twice weekly until liver chemistry test abnormalities resolve, stabilize, or return to baseline • A specialist or hepatology consultation is recommended 
If ALT or AST $\geq 3 \times \text{ULN}$ AND total bilirubin $< 2 \times \text{ULN}$ and INR ≤ 1.5:
 
 • Repeat liver chemistry tests (include ALT, AST, alkaline phosphatase, total bilirubin and INR) and perform liver chemistry follow-up assessments within 24 to 72 hours • Monitor participants weekly until liver chemistry abnormalities resolve, stabilize, or return to baseline 
RESTART/RECHALLENGE
	
 • Viral hepatitis serology⁴ • Obtain blood sample for PK-analysis as quick as possible after the most recent dose⁴ • Obtain serum creatine phosphokinase (CPK), lactate dehydrogenase (LDH), gamma-glutamyltransferase [GGT], and glutamate dehydrogenase [GLDH], and serum albumin • Fractionate bilirubin if total bilirubin $\geq 2 \times \text{ULN}$ • Obtain complete blood count with differential to assess eosinophilia • Record the appearance or worsening of clinical symptoms of liver injury, or hypersensitivity, on the liver event reporting form • Record use of concomitant medications (including acetaminophen, herbal remedies, recreational drugs, and other over-the-counter medications) • Record alcohol use on the liver event alcohol intake form 
If ALT or AST $\geq 3 \times \text{ULN}$ AND total bilirubin $\geq 2 \times \text{ULN}$ or INR > 1.5 obtain the following in addition to the assessments listed above:
 
 • Anti-nuclear antibody, anti-smooth muscle antibody, Type 1 anti-liver kidney microsomal antibodies, and quantitative total immunoglobulin G (IgG) or gamma globulins • Serum acetaminophen adduct assay, when available, to assess potential acetaminophen contribution to liver injury in participants with definite or likely acetaminophen use in the preceding week

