

 • Do not restart/rechallenge participant with study intervention unless allowed per protocol and sponsor approval is granted • If restart/rechallenge not allowed per protocol or not granted, permanently discontinue study intervention and continue participant in the study for any protocol specified follow up assessments 	
 • Liver imaging (ultrasound, magnetic resonance, or computerized tomography) to evaluate liver disease; complete the liver imaging form • Liver biopsy may be considered and discussed with local specialist if available, for instance: 
 – In patients when serology raises the possibility of autoimmune hepatitis (AIH) – In patients when suspected DILI progresses or fails to resolve on withdrawal of study intervention – In patients with acute or chronic atypical presentation • If liver biopsy conducted complete the liver biopsy form
---	--

1. Serum bilirubin fractionation should be performed if testing is available. If serum bilirubin fractionation is not immediately available, discontinue study intervention if ALT or AST $\geq 3 \times \text{ULN}$ **and** total bilirubin $\geq 2 \times \text{ULN}$. Additionally, if serum bilirubin fractionation testing is unavailable, **record the absence/presence of detectable urinary bilirubin on dipstick** which is indicative of direct bilirubin elevations suggesting liver injury.
2. All events of ALT or AST $\geq 3 \times \text{ULN}$ **and** total bilirubin $\geq 2 \times \text{ULN}$ ($> 35\%$ direct bilirubin) or ALT or AST $\geq 3 \times \text{ULN}$ **and** INR > 1.5 may indicate severe liver injury (**possible 'Hy's Law'**) and **must be reported to sponsor in an expedited manner and as an SAE if SAE criteria met (excluding studies of hepatic impairment or cirrhosis)**. The INR stated threshold value will not apply to participants receiving anticoagulants.
3. New or worsening symptoms believed to be related to liver injury (such as fatigue, nausea, vomiting, right upper quadrant pain or tenderness, or jaundice) or hypersensitivity (such as fever, rash or eosinophilia).

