4. PK sample may not be required for participants known to be receiving placebo or non-comparator interventions. Record the date/time of the PK blood sample draw and the date/time of the last dose of study intervention prior to the PK blood sample draw on the CRF. If the date or time of the last dose is unclear, provide the participant's best approximation. If the date/time of the last dose cannot be approximated OR a PK sample cannot be collected in the time period indicated above, do not obtain a PK sample. Instructions for sample handling and shipping are included in the pertinent Study Reference Manual.

Liver Chemistry Increased Monitoring Criteria with Continued Study Intervention

Liver Chemistry Increased Monitoring Criteria and Actions with Continued Study Intervention	
Criteria	Actions

ALT or AST $\geq 5 \times \text{ULN}$ and $< 8 \times \text{ULN}$ and total bilirubin $< 2 \times \text{ULN}$ or INR < 1.5 without symptoms believed to be related to liver injury or hypersensitivity, and who can be monitored weekly for 2 weeks
 
OR
 
ALT or AST $\geq 3 \times \text{ULN}$ and $< 5 \times \text{ULN}$ and total bilirubin $< 2 \times \text{ULN}$ or INR < 1.5 without symptoms believed to be related to liver injury or hypersensitivity, and who can be monitored weekly for 4 weeks
	
 • Notify the sponsor within 24 hours of learning of the abnormality to discuss participant safety • Participant must return weekly for repeat liver chemistry tests (ALT, AST, alkaline phosphatase, total bilirubin) until the abnormalities resolve, stabilize, or return to baseline • If at any time the participant meets liver chemistry stopping criteria proceed as described in the pertinent manual • If ALT or AST decreases from ALT or AST $\geq 5 \times \text{ULN}$ and $< 8 \times \text{ULN}$ to $\geq 3 \times \text{ULN}$ but $< 5 \times \text{ULN}$, continue to monitor liver chemistries weekly • If, after 4 weeks of monitoring, ALT or AST $< 3 \times \text{ULN}$ and total bilirubin $< 2 \times \text{ULN}$, monitor participants twice monthly until liver chemistry tests resolve, stabilize, or return to baseline

References:

EASL Clinical Practice Guidelines: Drug-induced liver injury. *Journal of Hepatology* 2019; 70 (6):1222-1261.

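### Attachment 8B counts a raised-bilirubin Hy's law case only if more than 35% of the bilirubin is direct; Section 12.3.2 requires the SAE form without that condition (minor)

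*Protocol*

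**What the plan says.** **Protocol Section 12.3.2** treats any possible Hy's law case as an important medical event. The definition is AST or ALT ≥3×ULN together with bilirubin ≥2×ULN or INR >1.5, with INR disregarded in subjects on anticoagulants. Each such case "must be reported to the sponsor in an expedited manner using the Serious Adverse Event form", and this applies "even before all other possible causes of liver injury have been excluded". SAEs are due to the sponsor within 24 hours of site awareness.

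**Attachment 8B, footnote 2**, uses the same Hy's law label. Its bilirubin limb, however, is ALT or AST ≥3×ULN and total bilirubin ≥2×ULN with more than 35% direct bilirubin. Such events "must be reported to sponsor in an expedited manner and as an SAE if SAE criteria met". The footnote is attached to the bilirubin and INR stopping rows, and also to the line in the actions list about completing an SAE form.

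**Attachment 8B, footnote 1**, drops the direct-fraction condition in one situation: "If serum bilirubin fractionation is not immediately available, discontinue study intervention if ALT or AST" is ≥3×ULN and total bilirubin is ≥2×ULN. That fallback concerns stopping drug, not reporting. The same footnote describes urinary bilirubin on dipstick as a finding "which is indicative of direct bilirubin elevations suggesting liver injury".

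**Attachment 8B, monitoring and follow-up**, separates two tiers by total bilirubin. At ≥2×ULN or INR >1.5 the subject is monitored twice weekly; at <2×ULN *and* INR ≤1.5, weekly. The follow-up list adds "Fractionate bilirubin if total bilirubin" is ≥2×ULN.

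**Attachment 8B, increased monitoring with continued dosing**, admits subjects with total bilirubin <2×ULN *or* INR <1.5 in both of its ALT/AST bands. The upper band (5 to below 8×ULN) is for those "without symptoms believed to be related to liver injury or hypersensitivity, and who can be monitored weekly for 2 weeks"; the lower band (3 to below 5×ULN) allows 4 weeks.

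**The concern.** One safety term has two definitions in current text. The 35% condition sorts cases by likely liver origin, and Section 12.3.2 says reporting must not wait for that sorting. A site that takes its definition from footnote 2 could leave out an SAE form that Section 12.3.2 requires, and the event would then be missing from the SAE tables.

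The *or* in the increased-monitoring table is a second, separate slip. A subject whose bilirubin is well above 2×ULN satisfies it through a normal INR alone, and so appears eligible to continue dosing with weekly rather than twice-weekly tests.

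**Working it through.** No figure in the plan needs reproducing. The check applies each visible rule to two example cases.

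Assumptions: a direct fraction has been measured, there are no symptoms, weekly monitoring is possible, and the elevation has not yet lasted long enough to meet a persistence row. The 8A figure is not available and is left out.

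- Case A: ALT 4×ULN, total bilirubin 2.5×ULN, 30% direct, INR 1.2.
- Case B: ALT 4×ULN, total bilirubin 5×ULN, 50% direct, INR 1.2.

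| Rule | Case A | Case B |
|---|---|---|
| Section 12.3.2: ALT ≥3 and (bilirubin ≥2 or INR >1.5) | 4 ≥ 3 and 2.5 ≥ 2: SAE form | 4 ≥ 3 and 5 ≥ 2: SAE form |
| 8B footnote 2: bilirubin ≥2 with direct >35%, or INR >1.5 | 30% is not >35%, 1.2 is not >1.5: not counted | 50% > 35%: counted |
| 8B immediate stopping rows | not met (4 < 8; 30% direct; INR 1.2) | met (bilirubin row) |
| 8B twice-weekly tier: bilirubin ≥2 or INR >1.5 | within it | within it |
| Increased monitoring with *or*: bilirubin <2 or INR <1.5 | 1.2 < 1.5: admitted | 1.2 < 1.5: admitted |
| Same with *and* | 2.5 is not <2: not admitted | 5 is not <2: not admitted |

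**Reporting.** The two definitions differ only for cases like A: total bilirubin ≥2×ULN, direct fraction 35% or less, INR not above 1.5. If INR exceeds 1.5, both texts count the case (anticoagulants aside). If the direct fraction exceeds 35%, both count it.

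**Order of events.** The chemistry panel in Section 9.6 lists total bilirubin, with no direct bilirubin and no INR. Section 12.3.2 is therefore triggered by the total result. Fractionation is a follow-up test prompted by that same result, so on the normal path the SAE form is already due before a direct fraction exists.

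**The *or*.** Case B is admitted to continued dosing and is also a stopping case, so the literal *or* contradicts the stopping table. With *and*, the contradiction goes and the wording matches the monitoring tiers. Case B is stopped in either event, because 8B discontinues anyone who meets a stopping row. Case A is the one the literal *or* would keep on drug with weekly tests.

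**After the correction.** With *and*, Case A is in neither the immediate stopping rows nor the increased-monitoring table. The 24-hour sponsor notices in 8B belong to those two routes, so in the visible text the clear 24-hour duty for Case A is the one in Section 12.3.2.

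**The case against.** The best case on the other side is that nothing truly conflicts. Footnote 2 says which events must be reported; it does not say that others need not be. It annotates stopping rows and repeats their wording. Section 12.3.2 is the protocol's SAE-reporting section, is broader and mandatory, and a site that follows it satisfies both texts. It also acts first, on total bilirubin. Section 10.2 sends investigators to 8A for stopping conditions and to 8B for follow-up and restart guidance, not for SAE reporting. The 8A figure might address the case.

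Most of this stands, and it limits the size of the point. It does not remove it: the SAE line in 8B's own actions list carries the mark for footnote 2, so that narrower definition is what a site working through 8B will read on this question.

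A reader might go further and make three inferences that the documents do not support:

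- That footnote 2 exempts low-direct cases from SAE reporting. It contains no such exemption.
- That making SAE reporting conditional on SAE criteria is a second conflict. Section 12.3.2 calls every such case an important medical event, and medical importance is an SAE criterion in Section 12.1.1, so this is only a missing cross-reference.
- In the reassuring direction, that the sponsor hears within 24 hours whichever text is followed. Once the *or* is read as *and*, 8B gives no clear 24-hour route for Case A.

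**Conclusion.** Wrong as written, and minor. Footnote 2 leaves out one case type that Section 12.3.2 requires on the SAE form, and the increased-monitoring criteria use *or* where the rest of 8B calls for *and*. The first matters only if a site relies on footnote 2 alone after a direct fraction is known. The second matters for low-direct cases, since subjects who meet a stopping row are still stopped.

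It would be too strong to conclude that an SAE has been missed or that trial results are affected. The documents show no such case and give no frequency, so no expected number can be stated. The primary analysis, sample size and error rate are untouched.

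The conclusion rests on the visible text of Section 12.3.2 and Attachment 8B. The 8A figure could confirm or complicate the handling of low-direct cases, but it would not change the two differing definitions.

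**What to change.** 1. In footnote 2, remove the 35% direct-bilirubin condition for reporting, and replace the conditional SAE wording with a reference to the SAE form under Section 12.3.2. Keep the 35% condition only as a stopping criterion in the 8B table.
2. In both criteria of the increased-monitoring table, change *or* to *and*. Use INR ≤1.5 there, as in the weekly tier; otherwise an INR of exactly 1.5 is in neither that table nor the INR stopping row.
3. Add one line: a case with total bilirubin ≥2×ULN and 35% or less direct follows the twice-weekly monitoring and 24-hour sponsor notification, with stopping at the investigator's discretion under Section 10.2.
4. Check that the 8A figure agrees.

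The cost is a few words and one line, but Section 17.1 requires a formal amendment, with ethics committee approval unless the change is purely logistic or administrative. No analysis changes.

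Section 3.1 planned the study to stop in Q1 2025, so new wording may guide few or no further cases. An optional way to apply the same rule is to check existing results, including any from local laboratories, for ALT or AST ≥3×ULN with total bilirubin ≥2×ULN, and confirm that each case found was recorded as an SAE. The Section 12.3.2 wording dates from Amendment 5 (10 June 2021); earlier cases should be judged under Section 12.1.1. The search is small for later study phases: the Part 3 SAP states that no scheduled laboratory tests were done during withdrawal, and the re-treatment SAP lists them only at R0, R16 and R28.
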